7.1 COVID-19 Impact

No changes to the planned analysis of the efficacy endpoints will be performed due to the impact of COVID-19 outbreak.

Instead, additional outputs will be generated to assess potential impacts of COVID-19 to this study including:

- Listing of participants potentially affected by pandemic and with any AEs or PDs related to COVID-19
- Listing of participants with any missed treatment administrations, tumor assessments or missed visits due to COVID-19
- Listing of PDs related to COVID-19
- Listing of AEs related to COVID-19
- Table of COVID-19 vaccinations
- Listing of COVID-19 vaccinations
- Table of TEAEs associated with the vaccination for COVID-19 (in case that AEs associated with COVID-19 vaccination will be observed for 10 subjects or more)
- Listing of AEs related to COVID-19 vaccination.

8 Analysis Populations and Subgroups

8.1 Definition of Analysis Populations

Screening Analysis Set (SCR)

All participants who signed the informed consent.

Full Analysis Set (FAS)/Safety Analysis Set (SAF)

The Full Analysis Set as well as the Safety Analysis Set include all participants who were administered at least 1 infusion of bintrafusp alfa.

The FAS terminology will be used for all analyses of demographics and baseline characteristics, efficacy, CCI [REDACTED]. The SAF terminology will be used for all exposure and safety analyses.

Pharmacokinetic Analysis Set (PKAS)

The Pharmacokinetic Analysis Set (PKAS) includes all participants who complete at least one infusion of bintrafusp alfa, and who provide at least one sample with a measurable concentration of bintrafusp alfa, without important protocol deviations or events deemed to affect PK evaluation.

All PK analyses will be based on this analysis set. Refer to Section 10.2 and Section 16.1.1 for handling of protocol deviations relevant to PK.

Pharmacokinetic ADA Analysis Set (PKADA)

A subpopulation of the PKAS restricted to subjects who have in addition at least one valid result of antidrug antibody (ADA) at any time point.

Pharmacokinetic nAb Analysis Set (PKNAB)

A subpopulation of the PKAS restricted to subjects who have in addition at least one valid result of neutralizing anti-drug antibodies (nAb) at any time point.

Immunogenicity analysis set (IMM)

All participants who were administered at least one infusion of bintrafusp alfa and have at least one valid ADA result. All ADA analyses will be based on this analysis set.

Table 3 displays the use of the analysis sets in the different analyses:

Table 3 Overview of the Analysis Set Used in the Analyses

Analyses	SCR	SAF	FAS	PK	PKA DA	PKN AB	IMM
Disposition	✓						
Demographics			✓				
Baseline Assessments			✓				
Previous and Concomitant Therapies			✓				
Compliance and Exposure		✓					
Efficacy			✓				
Safety and Tolerability		✓					
Pharmacokinetics				✓	✓	✓	
CCI	CCI						
Immunogenicity							✓
CCI	CCI						

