
ADA=antidrug antibody, AE=adverse event, DOR=duration of response, DRR=durable response rate, IRC=Independent Review Committee, NCI-CTCAE v5.0=National Cancer Institute-Common Terminology Criteria for Adverse Events v5.0, OS =overall survival, PD-L1=programmed death-ligand 1, ORR=objective response rates, PFS=progression-free survival, PK=pharmacokinetic, RECIST 1.1=Response Evaluation Criteria in Solid Tumors Version 1.1, TEAE=Treatment-emergent adverse event.
	

Overall Design: This Phase II, multicenter, international, single-arm study is to evaluate bintrafusp alfa monotherapy in participants with advanced unresectable and/or metastatic cervical cancer with disease progression during or after platinum-based chemotherapy.

The study plans to enroll approximately 135 eligible participants from multiple study sites globally. The study is intended to enroll at least 15% of participants from China. After reaching the completion of the global study enrollment, if the number of participants enrolled in China does not meet the 15% target, enrollment may continue in China to meet local requirement until the target (at least 15%) participants from China is met.

Participants will receive an intravenous (IV) infusion of bintrafusp alfa at a dose of 1200 mg over 1 hour (-10 minutes/+ 20 minutes, i.e., over 50 to 80 minutes) once every 2 weeks.

The study includes:

- 28-day Screening period.
- Treatment with bintrafusp alfa at a dose of 1200 mg once every 2 weeks until confirmed progressive disease (PD) per Response Evaluation Criteria in Solid Tumors Version 1.1 (RECIST 1.1), death, unacceptable toxicity, or study withdrawal.
 - In the case of PD, treatment may continue if the participant's performance status (PS) has remained at least stable, in the opinion of the Investigator, the participant may benefit from continued treatment, and if other criteria are fulfilled as outlined in the protocol (refer to Section 7.1.3).
 - Participants who have experienced a confirmed complete response (CR) should continue treatment for a maximum of 24 months after confirmation of response (at the discretion of the Investigator). If the Investigator believes that a participant with confirmed CR may benefit from treatment beyond 24 months, it may be permissible to continue treatment after discussion with the Medical Monitor and the Sponsor's Medical Responsible.

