9.3 Populations for Analyses

The analyses populations are specified below. The final decision to exclude participants from any analysis population will be made and documented during a data review meeting prior to database lock.

The analysis will be performed on approximately 135 patients globally. China participants (whether enrolled before or after the completion of the global enrollment) may be analyzed separately per local regulatory requirements, and follow the same definition as Section 4.1.

For purposes of analysis, the analysis populations are defined in [Table 11](#).

Table 11 Analysis Populations

Screening (SCR)	All participants, who provided informed consent, regardless of the participant's study intervention status in the study.
Safety (SAF)/ Full Analysis Set (FAS)	All participants, who were administered at least 1 infusion of bintrafusp alfa. The primary analysis population for efficacy and CCI analyses is the Full Analysis Set. The primary analysis population for all analyses of safety and health-related quality of life is the Safety population.
Pharmacokinetic (PK)	All participants who complete at least 1 infusion of bintrafusp alfa, and who provide at least 1 sample with a measurable concentration of bintrafusp alfa.
Immunogenicity Analysis Set (IMM)	All participants who were administered at least 1 infusion of bintrafusp alfa and have at least one valid ADA result. All ADA analyses will be based on this analysis set.

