9.4.4 Sequence of Analyses

The planned efficacy analyses are specified below. Details of all planned analyses will be defined in the IAP:

- The interim analysis on objective response will be performed 6 months after 81 participants have been enrolled. At the same time, the analysis of durable response of at least 6 months will be performed to support the ORR data and confirm that the responses are durable.
- The primary analysis on objective response will be performed 12 months after the accrual of the last planned global participant. At the same time, the analysis of durable response of at least 6 months will be performed to support the ORR data and confirm that the responses are durable. The analysis of DOR and PFS will be performed as well to support efficacy assessment of bintrafusp alfa.
- CCI [REDACTED]
- A separate analysis of key endpoints of ORR, DOR and OS may be performed in the subgroup of Chinese participants per local regulatory requirements once the cutoff criteria mentioned above are met for this subgroup (i.e., 12 months after accrual of the last Chinese participant for ORR, DOR and PFS and once at least 67% of Chinese participants have died for OS, respectively).
- If the study continues beyond 67% of the participants died (either globally or in the additional China enrollment), subsequent analyses may be performed.

10 References

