3.0	1July2021	PPD	
 - Update in section 7.1: 
 - listing of COVID-19 impact added - COVID-19 vaccination related outputs added - [Redacted] CCI - Update in section 8.2: 
 - describe analyses for China and Japan authorities - Number of prior treatment lines, Prior anti-cancer RT and HPV status by central lab definition updated for clarification - ADA treatment-emergent status added - Section 9.1 Data Handling After Cut-off Date - [Redacted] CCI - Section 9.9 added some clarifications on Rules to define previous and/or concomitant medication table - Updated section 9.11 Moore criteria - Updated section 10.2.1: Important Protocol Deviations reporting - Section 11.3.2: added clarification for HPV calculation - Updated section 12.4 Previous anticancer treatments and procedures including CCRT description - Updated section 13 Cumulative dose and relative dose intensity formulas - Section 14 Non-CR/Non-PD options added for BOR calculations - Section 14.1.1 waterfall with subgroups added - Updated section 14.2.4 censoring reasons categories - Section 15.4 removed "except oxygen saturation" - Updated section 16.3 - [Redacted] CCI - Longitudinal analysis of change from baseline - Updated Section 16.4 Immunogenicity analyses - [Redacted] CCI
4.0	21February2022	PPD	
 - Section 6: Added "Overview of Planned Analyses after discontinuation of NSCLC and BTC trials"

4 Purpose of the Integrated Analysis Plan

The purpose of this integrated analysis plan (IAP) is to document technical and detailed specifications for interim, primary and final analyses of data collected for protocol MS200647_0017.

Results of the analyses described in this IAP will be included in the Clinical Study Report (CSR). Additionally, the planned analyses identified in this IAP may be included in regulatory submissions or future manuscripts. Any post-hoc, or unplanned analyses performed to provide results for inclusion in the CSR but not identified in this prospective IAP will be clearly identified in the CSR.

The IAP is based upon Section 9 (Statistical Considerations) of the study protocol and is prepared in compliance with International Council for Harmonization (ICH) Guideline E9. It describes analyses planned in the protocol.

5 Objectives and Endpoints

Table 1 Study Objectives and Endpoints

Objectives	Endpoints (Outcome Measures)	IAP section
Primary		

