Table 2 Overview of Analyses

CCI			
Interim analysis (IA)	CCI	
 81 first dosed participants All dosed participants (all analyses except efficacy analyses) 	
 Participant disposition Demographics Medical history Previous and subsequent anticancer medications and other baseline characteristics (disease history, Eastern Cooperative Oncology Group Performance Status [ECOG PS]) Concomitant medications Treatment compliance and exposure Confirmed objective response as adjudicated by IRC Progression-free survival (PFS) as adjudicated by IRC Duration of response (DOR) as adjudicated by IRC Durable response rate (DRR) as adjudicated by IRC ORR, DoR and PFS based on investigator assessment Safety analyses (Adverse events (AEs), deaths, vital signs and clinical laboratory evaluations)
Primary analysis (PA)	CCI	All participants	Full evaluation of all efficacy and safety endpoints
Final analysis (FA)	CCI	All participants	Full evaluation of all efficacy and safety endpoints for the data that will be updated after PA

If key results presented during the IA are positive, meaning a lower bound of the exact 95% confidence interval (CI) for ORR is above 15% based on 81 participants, a full evaluation of all

efficacy and safety endpoints will be also provided at this time. In case the recruitment between the 81st and the last global participants is going fast and the timing between IA and PA is getting close, the possibility to not perform the IA will be discussed.

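### The SAP does not carry over the protocol's limit of the main ORR analysis to the global cohort, so late China-extension participants could enter the denominator with no time to confirm a response

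*SAP*

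**What the plan says.** **Protocol.** The Synopsis allows that, if fewer than 15% of participants come from China when global enrolment closes, "enrollment may continue in China to meet local requirement until the target" is reached. Section 9.3 sets the scope of the main analysis: "The analysis will be performed on approximately 135 patients globally". It adds that "China participants (whether enrolled before or after the completion of the global enrollment) may be analyzed separately per local regulatory requirements". Section 9.4.4 times the primary response analysis "12 months after the accrual of the last planned global participant" and allows a China analysis 12 months after the last Chinese participant. Table 11 in Section 9.3 defines the FAS and the safety set (SAF) alike, as everyone given at least one infusion.

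**SAP.** Section 4 states that "The IAP is based upon Section 9 (Statistical Considerations) of the study protocol". Section 8.1 says the FAS and SAF "include all participants who were administered at least 1 infusion of bintrafusp alfa", and Table 3 assigns efficacy to the FAS. Section 6, Table 2 limits interim efficacy to the "81 first dosed participants", but for the primary analysis it lists "All participants". Section 8.2 defines a China sub-population by site, in which a subset of outputs may be repeated. It does not take extension participants out of the main set. Section 6.1 (SAP version 4.0) replaces the Table 2 programme with one analysis at 15 February 2022, described as the primary analysis cut-off. That analysis still includes the IRC and Investigator ORR.

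**The concern.** The SAP is what the programmer follows. Read literally, its primary ORR denominator is everyone dosed by the cut-off, including anyone enrolled in China after global enrolment closed. The cut-off is tied to the last global participant, so every extension participant has less than 12 months of follow-up by then, and the latest have only weeks.

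A confirmed response needs two qualifying assessments at least 4 weeks apart (SAP 14.1.1). Someone dosed too late for a second scan ends up as stable disease, progression or not evaluable. All three stay in the denominator as non-responders. The success rule asks whether the lower limit of the exact 95% interval exceeds 15%, so a few such participants could matter when the result is close to the threshold. An unstated denominator could also end up being settled after the data are seen.

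**Working it through.** **Method check.** The design ORR, power and precision tables are redacted, so the sample size of 135 cannot be re-derived. The exact Clopper-Pearson method does reproduce the intervals quoted in protocol 2.2: 6/25 gives 9.4–45.1%, 7/25 gives 12.1–49.4%, 12/98 gives 6.5–20.4%, 11/77 gives 7.4–24.1% and 5/19 gives 9.1–51.2%.

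**Who is too late.** SAP 14.2.4 puts the second planned scan at 16 weeks, and SAP 14.1.1 refers to an 8-week assessment. The earliest confirmed response therefore comes at about 8 + 4 = 12 weeks, or 16 weeks on scheduled scans. With the cut-off 52 weeks after the last global participant, only those first dosed some 36 to 40 weeks or more after that participant (roughly 8 to 9 months) cannot confirm.

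**How large the extension could be.** Take the smallest x with (k + x)/(135 + x) ≥ 0.15, where k is the number from China among the 135. The documents do not give k, so it is assumed:
- k = 0: x = 24 (24/159 = 15.1%)
- k = 10: x = 13 (23/148 = 15.5%)
- k = 15: x = 7 (22/142 = 15.5%)
- k ≥ 21: x = 0

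**Success bar in the global cohort.** The smallest number of responders out of 135 with an exact lower limit above 15% is 30 (22.2%, interval 15.5–30.2%).

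**Adding participants who cannot respond.**
- 30/139: lower limit 15.06%, success
- 30/140: lower limit 14.95%, failure
- 30/159: 18.9%, lower limit 13.1%, failure

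Overturning a success takes 5 such additions with 30 responders, 11 with 31, 16 with 32, 22 with 33 and 27 with 34. So 34 or more responders among the 135 cannot be overturned by an extension of up to 24.

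**Chance of success.** This assumes a true ORR of 25%; Phase I observed 24.0%. The formula is P(X ≥ bar) with X ~ Bin(135 + added − too late, 0.25), where the bar is that for n = 135 + added.

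| Added | Too late | Bar | Chance of success |
|---|---|---|---|
| 0 | 0 | 30 | 80.0% |
| 10 | 10 | 31 | 73.8% |
| 24 | 24 | 34 | 51.3% |
| 24 | 8 | 34 | 78.6% |
| 24 | 6 | 34 | about 81% |
| 13 | 4 | 32 | 80.6% |
| 24 | 0 | 34 | 87.5% |

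The large drops need every added participant to be too late. When most have enough follow-up, the extra responders roughly offset the loss or more than offset it.

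**The case against.** The strongest reply is that the protocol already settles the scope. Its own Table 11 uses the same all-dosed definition, yet Section 9.3 limits the analysis to about 135 global participants. The definition of the FAS was therefore never meant to fix the scope, and the SAP says it rests on that section. SAP Section 6 also mentions the last global participants when it discusses timing. The Table 2 cut-off cells, SAP Section 7 and protocol 9.2 are redacted and could contain the restriction. This stands as far as intent goes: a reader might infer that extension participants would certainly enter the primary ORR, and the documents do not support that. They could enter if the SAP is applied without protocol 9.3. The readable SAP still lacks the limit, although it restricts the interim efficacy set explicitly.

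Three other stronger readings also fail:
- A reader might take 24 late participants, or a fall in the chance of success to 51.3%, as the expected effect. That is an extreme case, and nothing in the documents says the extension took place.
- A reader might extend the bias to the durable response rate. Short follow-up would count against that endpoint, but it is not in the list of analyses kept by SAP 6.1.
- A reader might fear a false-positive claim. The effect of late participants on the ORR is downward.

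The supplementary count of recent unconfirmed responses in SAP 14.1.1 would make the problem visible, but it does not change the denominator.

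**Conclusion.** The point holds as a mismatch between the protocol and the readable SAP, with a conditional effect. It bites only if the China extension opens, its participants are dosed before the primary cut-off, and some are first dosed in the last 12 to 16 weeks or so. The primary IRC ORR would then be biased downward. Five such participants are enough to reverse a result of exactly 30 responders, and none of the extension sizes considered (up to 24) reverses 34 or more. If most extension participants have adequate follow-up, the chance of success hardly changes or rises. If the extension is not used, there is no effect. The result rests on the inferred 8-week scan interval and, for the probabilities, on the assumed 25% true rate. It is worth correcting because the remedy is small and fixes the denominator in advance.

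**What to change.** In SAP 8.1, and for the single analysis in SAP 6.1, state that the main efficacy analyses (IRC and Investigator ORR, DOR, PFS and OS) use dosed participants enrolled up to and including the last planned global participant. Report the efficacy of extension participants only in the China sub-population, at its own cut-off as in protocol 9.4.4. Leave the SAF as all dosed participants, so that no one is lost from the safety tables, and leave the interim efficacy set (first 81 dosed) unchanged.

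The cost is one sentence and one population flag. The protocol makes the China analysis optional, and SAP 6.1 plans no further analysis unless a new safety signal appears. If the extension was used, Section 6.1 should therefore also say whether the China analysis will still be done. If it was not used, saying so closes the point.

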8.2 Subgroup Definition and Parameterization

Analysis of primary and key secondary efficacy endpoints may be performed on subgroups of interest as specified in this IAP Section 14. CCI

For the definition of subgroup level, data as documented in the electronic case report form (eCRF) will be taken. The category “missing” will not be included in any subgroup analysis.

In case of low number of participants within a category (< 7 participants, which is about 5% of the randomized population), categories will be pooled when meaningful.

The following subgroups will be defined and used for the subgroup efficacy analyses:

- Age
 - Age \geq 18 - < 50 years
 - Age \geq 50 - < 65 years
 - Age \geq 65 years
- Moore criteria
 - Low
 - Medium
 - High
 - Unknown
- Histology
 - Squamous cell carcinoma
 - Adenocarcinoma
 - Adenosquamous cell carcinoma
- Number of prior treatment lines (metastatic/locally advanced prior anti-cancer drug therapies (see Section 12.4))
 - 0
 - 1
 - 2
 - 3
 - \geq 4
- Pooled Region
 - North America
 - Europe
 - South America
 - Asia
 - Rest of the World (RoW)
- Prior Bevacizumab use

- Yes
 - No
- Prior anti-cancer radiotherapy (see Section 12.4)
 - Yes
 - No
- ADA status
 - Ever positive
 - Never positive
- ADA treatment-emergent status
 - Treatment-emergent ALL
- Non-treatment-emergent nAb status
 - Ever positive (for either assay TGF- β or PD-L1)
 - Never positive

All subgroups are associated with demographic and clinical variables corresponding with cervical cancer prognosis except ADA and nAb status.

For ADA and nAb status subgroups, the subgroup analyses will be performed if there are at least 3 ever positive participants.

The subgroups coming from the individual items composing the Moore criteria will be defined and used only for the Objective Response Rate (ORR) and Duration of Response (DOR) subgroup analyses:

- ECOG PS at baseline
 - ECOG PS 0
 - ECOG PS 1
- RACE from Moore criteria
 - Black or African American
 - Not Black or African American
- RACE
 - White
 - Black or African American
 - Chinese
 - Japanese
 - Korean

- Other Asian
 - Other
- Measurable disease in pelvis
 - Yes
 - No
- Disease progression-free interval from date of diagnosis < 1 year
 - Yes
 - No
- Prior platinum therapy exposure to radiotherapy
 - Yes
 - No

CCI

- PD-L1 expression at baseline measured by central lab:
 - PD-L1 expression in tumor tissue measured by 22C3 (CPS \geq 1, < 1, NE or NA)
 - PD-L1 expression in tumor tissue measured by SP263 (vCPS (Visual element Combined Positive Score (Ventana)) \geq 5%, < 5%, NE or NA)
- HPV status collected on the “Disease History” eCRF page
 - HPV16+ or HPV18+
 - HPV+ (all other subtypes)
 - HPV-
 - Not done
- HPV status at baseline measured by central lab (see section 11.3.2)
 - High risk HPV+
 - Low Risk HPV+
 - HPV-
 - Not done

For HPV status collected on the eCRF, as they are several possibilities of testing (tumor, pre-malignant cervical lesion and other), it will be enough for a participant to have one positive value in one of the three tests to be in the associated subgroup.

CCI

To support submission purposes a subset of outputs may be repeated for the sub-populations described below:

- China: A Chinese participant is defined as a participant enrolled at a site in China
- Japan: A Japanese participant is defined as a participant enrolled at a site in Japan and of Japanese ethnicity as recorded in the case report form.

9 General Specifications for Data Analyses

This section describes any general specifications not included in subsequent sections.

Refer to Section 16.1 for PK data handling/analysis details.

The “start date” for this study is the start date of treatment.

Continuous (non-PK) variables will be summarized using descriptive statistics, i.e., the number of participants with non-missing values (n), arithmetic mean (Mean), standard deviation (StD), median (Med), 25th percentile (Q1) and 75th percentile (Q3), minimum (Min), and maximum (Max).

Qualitative variables will be summarized by frequency counts and percentages. Unless otherwise stated the calculation of proportions will be based on the number of participants of the analysis set of interest. Therefore, counts of missing observations will be included in the denominator and presented as a separate category.

Descriptive statistics by nominal visit or time point, e.g., for laboratory measurements, will include only data from scheduled visits. Unscheduled visits will be included in the derivation of baseline or worst on-treatment values.

Pharmacokinetic variables (concentrations and parameters) will also be summarized as described in Section 16.1.

The overall significance level is 2.5% one-sided. If CIs are to be calculated, these will be two-sided with a confidence probability of 95%, unless otherwise specified in this IAP.

In order to provide overall estimates of treatment effects, data will be pooled across sites. The “site” factor will not be considered in statistical models or for subgroup analyses due to the high number of participating sites in contrast to the anticipated small number of participants treated at each site.

All statistical analyses will be performed using SAS® Software Version 9.4 or higher in the SAS Grid environment (Statistical Analysis System, SAS-Institute, Cary NC, USA). The computer program Phoenix® WinNonlin® Version 8.0, or higher (Certara, L.P., Princeton, New Jersey, USA) could be used for PK data.

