6.1 Overview of Planned Analyses after discontinuation of NSCLC and BTC trials

The data review outcome from the 3 randomized controlled studies in NSCLC (Non-Small Cell Lung Cancer) and BTC (Biliary Tract Cancer) (MS200647-0005, MS200647-0037, MS200647_0055) appears to indicate, consistently across 2 indications, either poorer observed hazard ratios for PFS and OS in the experimental arms with bintrafusp alfa or low likelihood for bintrafusp alfa to add benefits compared to standard of care.

Based on this, the decision was made to restrict the analyses on this study MS200647-017. The analyses described in Table 2 will not be performed as planned, but one analysis based on the primary analysis cutoff of 15 February 2022 will be performed for an abbreviated CSR (aCSR).

The analyses considered relevant for this purpose are listed below:

- Participant disposition
- Important protocol deviations
- Demographics, medical history and other baseline characteristics (disease history, HPV and PD-L1 test at screening, vital signs at baseline, skin status history)
- Vaccines for COVID 19
- Previous and concomitant medications, procedures, follow-up treatments
- Treatment exposure and compliance
- Efficacy analyses:
 - ORR per RECIST 1.1 as assessed by IRC
 - ORR and DCR per RECIST 1.1 as assessed by IRC
 - Reasons for Non-evaluable BOR based on Confirmed Responses according to RECIST 1.1 as Adjudicated by IRC
 - Percent Change from Baseline in Sum of Diameters according to RECIST 1.1 as Adjudicated by IRC
 - Percent Change in Sum of Diameters between Baseline and Best Post-baseline Assessment according to RECIST 1.1 as Adjudicated by IRC and selected subgroups
 - ORR per RECIST 1.1 as assessed by IRC - Forest plot of odds ratio by subgroups
 - ORR and DCR per RECIST 1.1 as assessed by Investigator

- Concordant and Discordant Objective Response based on confirmed responses according to RECIST 1.1 between IRC and Investigator
- PFS per RECIST 1.1 as assessed by IRC
 - PFS per RECIST 1.1 as assessed by IRC - Kaplan-Meier Curve
 - PFS per RECIST 1.1 as assessed by IRC by histology and PD-L1 - Kaplan-Meier Curve
 - PFS per RECIST 1.1 as assessed by IRC - Forest plot of hazard ratio and free survival rates at 6 and 12 months by subgroups
 - PFS per irRECIST 1.1 as assessed by IRC - Kaplan-Meier Curve
- Duration of response per RECIST 1.1 as assessed by IRC
 - Duration of response per RECIST 1.1 as assessed by IRC - Kaplan-Meier Curve

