 - Time and Duration of Confirmed Response per Subject per RECIST 1.1 as assessed by IRC
- Overall survival (OS)
 - Overall survival - Kaplan-Meier Curve
 - Overall survival by histology and PD-L1 - Kaplan-Meier Curve
 - Overall Survival – Forest plot of hazard ratio by subgroups
- Follow-up time for Overall Survival (OS)

- Safety analyses (overview of treatment-emergent adverse events (TEAEs), serious TEAEs (SAE), treatment-related TEAEs, TEAEs leading to treatment discontinuation/interruption/modification, TEAEs Leading to death, adverse events of special interest (AESI), TEAEs associated to COVID-19, deaths, vital signs, ECOG, clinical laboratory evaluations).
- Pharmacokinetic Data

- Descriptive Statistics for Bintrafusp Alfa Serum CEOI and Ctough (<unit>) by Nominal Day
- Descriptive Statistics for Bintrafusp Alfa Serum Accumulation Ratios (RCEOI and RCtough) by Nominal Day
- Arithmetic Mean Bintrafusp Alpha Serum Trough Concentrations (Ctough) versus Nominal Day on Linear (\pm StD) Scale
- Geometric Mean Bintrafusp Alpha Serum Trough Concentrations (Ctough) versus Nominal Day on Linear (\pm logStD) Scale
- Median Bintrafusp Alpha Serum Trough Concentrations (Ctough) versus Nominal Day on Linear Scale
- Arithmetic Mean Bintrafusp Alpha Serum End of Infusion Concentrations (CEOI) versus Nominal Day on Linear (\pm StD) Scale
- Geometric Mean Bintrafusp Alpha Serum End of Infusion Concentrations (CEOI) versus Nominal Day on Linear (\pm logStD) Scale
- Median Bintrafusp Alpha Serum End of Infusion Concentrations (CEOI) versus Nominal Day on Linear Scale
- Individual Bintrafusp Alpha Serum Trough Concentrations (Ctough) versus Actual Day on Linear Scale
- Individual Bintrafusp Alpha Serum End of Infusion Concentrations (CEOI) versus Actual Day on Linear Scale

CCI

- Immunogenicity
 - Overview of ADA Subgroups
 - Listing of Subjects with Ever Positive ADA Results

In case a new safety signal is observed, an additional analysis will be done at end of study and included in a CSR addendum. In the other cases, no further analyses will be planned.

7 Changes to the Planned Analyses in the Clinical Study Protocol

CCI

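### ADA and nAb status, ascertained mostly after first dose, may appear as fixed subgroups in the ORR, PFS and OS forest plots, which would favour antibody-positive participants if positivity is acquired on treatment

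*SAP*

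**What the plan says.** **Subgroup list.** SAP 8.2 opens by permitting, not requiring, efficacy subgroup analyses, to the extent that Section 14 specifies them. Part of Section 14 is blacked out in the public copy. It then introduces its list with "The following subgroups will be defined and used for the subgroup efficacy analyses", and the list includes ADA ever/never positive, ADA treatment-emergent status and nAb ever/never positive. The only condition on the antibody rows is a count: "For ADA and nAb status subgroups, the subgroup analyses will be performed if there are at least 3 ever positive participants". They are set apart only as non-prognostic: "All subgroups are associated with demographic and clinical variables corresponding with cervical cancer prognosis except ADA and nAb status". Their timing is not mentioned.

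**Definitions.** In SAP 16.4.1.1 (Table 15) and 16.4.2 (Table 17), one positive result at any time makes a participant ever positive. For ADA, samples after treatment and during reinitiation count. Treatment-emergent status is post-baseline by construction. PFS (SAP 14.2.4) and OS (SAP 14.2.13) run from first dose.

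**Outputs now planned.** SAP 6.1 restricts the analysis: "The analyses described in Table 2 will not be performed as planned". It keeps, for ORR, "Forest plot of odds ratio by subgroups"; for PFS, "Forest plot of hazard ratio and free survival rates at 6 and 12 months by subgroups"; and for OS, "Forest plot of hazard ratio by subgroups". Under immunogenicity it keeps an ADA overview and "Listing of Subjects with Ever Positive ADA Results". It keeps no nAb output, and the efficacy-by-antibody evaluations of 16.4.1.1 and 16.4.2 are not on its list.

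**The concern.** A participant who converts on drug must stay under observation until the first positive sample. Someone who progresses early has few samples and tends to remain never positive. Comparing the two groups from day 1 credits the positives with time they had to survive in order to be classified (immortal-time bias).

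If such a row is printed, it can be read as the effect of antibodies on efficacy. It could look favourable when there is no effect, and could hide a harmful one. No readable text sets a landmark, a time-dependent status or a restriction to baseline status for these rows.

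**Working it through.** The plan states no figure on this point, so there is none to reproduce.

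**1. Sampling opportunity.** Protocol Table 2 schedules ADA samples pre-dose at weeks 1, 3, 5, 7 and 13, every 6 weeks to week 25, then every 12 weeks, plus end of treatment and 28 days later. Only week 1 is pre-treatment. Phase I treatment lasted a median of 9.6 weeks (range 2.0 to 72.0; protocol 2.2). Post-dose samples at those durations:
- 2.0 weeks: 0 scheduled + 2 = 2.
- 9.6 weeks: weeks 3, 5 and 7, + 2 = 5.
- 72 weeks: weeks 3, 5, 7, 13, 19, 25, 37, 49 and 61, + 2 = 11.

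**2. Hand check of direction.** Take exponential progression with the historical median PFS of 3.3 months (protocol 2.2), so λ = 0.693/3.3 = 0.21 per month. Assume conversion at μ = 0.03 per month until progression, with no effect on outcome.
- Mean PFS, never positive: 1/(λ+μ) = 1/0.24 = 4.17 months.
- Mean PFS, ever positive: 1/(λ+μ) + 1/λ = 4.17 + 4.76 = 8.93 months.
- Crude event-rate ratio: 4.17/8.93 = 0.47.

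The true ratio is 1. This idealised case has continuous sampling, none after progression and no baseline positives, so it shows direction only.

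**3. Simulation A: no antibody effect, Cox HR for PFS, ever versus never positive.** 1,500 trials of N = 135 per setting; Table 2 sampling; 8-weekly scans, later 12-weekly; cut-off 12 to 24 months. Assumed: 5% per month stop drug for other reasons, and median post-progression survival is 6 months. Cells show 0/5/20% pre-existing positives.

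| Conversion | Latent PFS median 2.1 months | Latent PFS median 3.3 months |
|---|---|---|
| 1% per month | 0.59/0.79/0.92 | 0.59/0.77/0.90 |
| 3% per month | 0.57/0.67/0.81 | 0.57/0.64/0.77 |
| 15% per month | 0.50/0.53/0.59 | 0.48/0.50/0.55 |
| Early, 15% convert within 10 weeks | 0.85/0.89/0.93 | 0.87/0.89/0.94 |
| Early, 30% convert within 10 weeks | 0.81/0.83/0.88 | 0.86/0.86/0.90 |

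With all positives pre-existing, the PFS HR is 1.00 to 1.04. OS HRs are 0.64 to 0.90 (3 to 15% per month) and 0.87 to 0.96 (early). Treatment-emergent status, induced only because boosting was not modelled, gives PFS 0.48 to 0.59 and 0.81 to 0.88.

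**4. Simulation B: separate assumptions, no antibody effect, all positivity acquired on treatment.** ORR 24% (Phase I); 30 to 50% of participants able to convert.

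| Median onset | ORR odds ratio | PFS HR | OS HR | Nominally significant PFS, n = 135 |
|---|---|---|---|---|
| 1 week | 1.06 | 0.95 | 0.94 | 3.7% |
| 4 weeks | 1.20 | 0.88 | 0.86 | 5.5% |
| 8 weeks | 1.53 | 0.78 | 0.76 | 14% |
| 16 weeks | 2.17 | 0.66 | 0.65 | 42% |
| 30 weeks | 2.70 | 0.59 | 0.59 | 58% |

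Check at 8 weeks: ORR 30.3% versus 22.1% gives (0.303/0.697)/(0.221/0.779) = 1.53. With 84% of positives pre-existing: OR 1.07, both HRs 0.96.

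**5. Treatment beyond progression** (allowed by protocol 7.1.3, not in A). A further simulation of 100,000 participants per setting reproduced the PFS pattern: 0.50 to 0.81 spread, 0.83 to 0.95 early. Letting all eligible participants continue for a mean of 3 months moved 0.59 to 0.67 (3% per month, none pre-existing) and the early range to 0.89 to 0.97.

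**6. Masking.** In A, a true progression HR of 1.5 after conversion reads 0.60 to 1.11 (3 to 15% per month) or 1.06 to 1.38 (early). A week-7 landmark reads 1.29 to 1.50 and 1.36 to 1.48.

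**7. Alternatives with no antibody effect.** Week-7 landmark in A: PFS 0.98 to 1.07, OS 0.98 to 1.05 (PFS 1.00 to 1.15 at 1% per month). Day-57 landmark in B, with an assay fully sensitive on drug and all positivity acquired: PFS 1.00 to 1.01, OS 0.99 to 1.01. Baseline status: PFS 1.00 to 1.07, OS 0.99 to 1.03 in A; 1.00 for both in B.

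**The case against.** **The rows may never be printed.** SAP 8.2 defers to Section 14, part of which is hidden. Where readable Section 14 names subgroups, for the waterfall plots, it omits ADA and nAb. SAP 6.1 names histology and PD-L1 for its Kaplan-Meier curves and keeps only an overview and a listing for immunogenicity. This stands: a reader might infer that the plan commits to these rows, and the documents do not support that. They do leave it open, because 6.1 narrows the subgroups for the waterfall and Kaplan-Meier displays but not for the forest plots. The nAb row is weaker still: 6.1 keeps no nAb output, and protocol 8.10 and 9.4.3 make nAb testing optional.

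**Acquisition is not shown.** A reader might also infer that positivity is largely acquired after dosing. The documents show only that it is largely ascertained then.

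**Early onset leaves little bias.** At a 4-week median onset, 5.5% nominal significance for PFS is close to chance. This stands.

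**Antibodies may be undetectable on drug.** B then gives OR 1.01 and PFS HR 0.99, though OS still reads 0.83. A gave PFS 0.55 to 0.92 in a similar setting. The two are not reconciled, so nothing here rests on that case. Protocol 9.4.3 plans an assay that works in the presence of drug.

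**Conclusion.** The concern holds conditionally. If the ADA rows are produced as defined and positivity is acquired on treatment, they favour ever-positive participants with no antibody effect. PFS HRs are about 0.5 to 0.8 with spread conversion and about 0.8 to 0.95 with early conversion, and nearer 1 with treatment beyond progression. The bias is close to none if positives are mostly pre-existing and, for ORR and PFS in simulation B, if the assay detects nothing on drug. Conversion rates, onset and baseline share are all assumed.

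The point is secondary and descriptive. No decision rule uses these rows, and the remaining output is one restricted analysis for an abbreviated report. A reader might infer that the headline efficacy result is compromised; it is not, because the primary ORR and its 15% threshold do not use antibody status. Low priority, but cheap to settle.

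**What to change.** State in SAP 6.1 and 8.2 that the ADA ever/never, ADA treatment-emergent and nAb ever/never rows are excluded from the ORR, PFS and OS forest plots, or replace them with baseline (pre-existing) status. This costs one line in each section.

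If an on-treatment comparison is wanted, pre-specify a landmark: for example, any positive sample up to and including week 7, among participants still event-free and in follow-up. It needs modest programming and no new data, since the week-7 sample is in protocol Table 2 and SAP 16.4.1.1 already derives the first-positive date.

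The landmark has costs. It ignores later conversions, and in simulation A about 5 to 8% of participants are lost to an event or censoring by then. Positives may be few: at 3% per month with none pre-existing, about 5. Even if everyone has an event, the 95% limits are then a factor of exp(1.96 × √(1/5 + 1/130)) = 2.4 either side. At the 8.2 minimum of 3 positives the factor is exp(1.96 × √(1/3 + 1/132)) = 3.1.

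Apply the same rule to 16.4.1.1 and 16.4.2 if those efficacy evaluations are ever run, and label any remaining ever/never efficacy display as descriptive and post-baseline.
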